7.2.4 EARLY TERMINATION VISIT

If a study subject's participation in the study is terminated early, an End of Study case report form must be completed. Data to be collected include:

- Reason for withdrawal / early termination
- Best corrected visual acuity (ETDRS)
- Applanation tonometry
- Slit lamp examination
- Indirect ophthalmic examination with dilated fundus exam
- Seidel's test
- Schirmer Tear Test
- · Lens status for phakic eyes
- Implant site photograph
- Body temperature
- Adverse events

7.2.5 SCHEDULE OF EVENTS TABLE

Table 3 Schedule of Events

Procedures	Screening/Baseline	Implant	Day 1	Week 1	Week 2	Month 1	Month 2	Month 3	Month 6, 12 & 24	Month 4.5, 8, 10, 15, 18, &21	Unscheduled
Informed Consent	Χ										
Eligibility Verification	Χ										
Medical History (including physical exam)	Х										
BGI Implant		X									
Best Corrected Visual Acuity (ETDRS)	Χ			X	Χ	Χ	Χ	X	Χ		Χ
Applanation Tonometry	Χ		Χ	X	Χ	Χ	Χ	X	Χ	Χ	Χ
Diurnal IOP	Χ								Χ		
Body Temperature	Χ		Χ	X	Χ	Χ	X	X	X		Χ
Central Corneal Thickness	Χ								X		
Slit Lamp Examination	Χ		Χ	X	Χ	Χ	Χ	X	Χ		Χ
Vertical C/D Ratio	Χ								Χ		
Corneal Surface Stain	Χ								Χ		
Indirect Ophthalmic Examination/Dilated Fundus Exam	X				Χ	Χ	X	Χ	X		X
Corneal Endothelial Cell Count	Χ							X	Χ		
Gonioscopy	Χ							X	X		
Optic Nerve Image Analysis	Х								X		
Perimetry of non implanted eye	Х								Х		
Seidel's Test		X	Χ	Χ	Χ	Χ	Χ	Χ	Χ	Χ	Χ
Schirmer Tear Test	Х					Χ		Χ	Х		
Lens Status for Phakic Eyes	Х					Χ		Χ	Χ		
Treatment Satisfaction Questionnaire	Х					Х		Х	Χ		
CIGTS	Χ					Χ		Χ	Χ		
Implant Site Photograph		X	Χ	Χ	Χ	Χ	Χ	Χ	Х	Х	Χ
Screening CRF	Х										
Implant CRF		Х									
Day 1 CRF			Χ								
Week 1 CRF				Χ							
Week 2/Month 2/Unscheduled CRF					Χ		Χ				Х
Month 1/Month 3 CRF						Χ		Χ			
Month 6/Month 12/Month 24 CRF									Χ		

Procedures	Screening/Baseline	Implant	Day 1	Week 1	Week 2	Month 1	Month 2	Month 3	Month 6, 12 & 24	Month 4.5, 8, 10, 15, 18, 821	Unscheduled
Month 4.5, 8, 10, 15, 18, and 21 CRD										X	
Adverse events		X	X	Χ	X	Χ	X	X	Χ	Χ	X
Medication Log	Χ	Χ	Χ	Χ	Χ	Χ	X	X	X	X	X
Device Experience CRF (if applicable)		Χ	Χ	Χ	Χ	Χ	Χ	X	X	X	X
Explantation CRF (if performed)		Χ	Χ	Χ	Χ	Χ	X	X	Χ	X	X
End of Study CRF (when conducted)		Х	Χ	Χ	Χ	Χ	X	X	Χ	X	X

7.3 CONCOMITANT MEDICATIONS, TREATMENTS, AND PROCEDURES

7.3.1 TREATMENT OF INFECTIONS

Since the MicroOptx Brown Glaucoma Implant is an externally communicating device, special care must be exercised to watch for and treat if necessary any ocular infections. The patient and care providers should be counseled on the signs of infection to watch for which include:

- Redness
- Ocular discomfort
- Headache
- Change in vision
- · Discharge at the implant site
- Device migration
- Changes in the external appearance of the eye
- Tissue hyperplasia at the implant site
- Hypopyon
- Hyphema
- Uveitis

Infections of the eye can rapidly damage important functional structures and lead to permanent vision loss or blindness. Any study subject presenting with signs and symptoms of endophthalmitis (hypopyon and anterior chamber cell and flare, with or without vitreous cell; pain, redness, etc) shall be urgently referred to a vitreo-retinal surgeon, where institutional best practices will be followed to obtain gram-stains, cultures and sensativities for suspected infections. Broad-spectrum antibiotics should be administered to the appropriate site of infection as soon as possible. Topical drops are preferred for corneal and conjunctival infections. Intravitreal antibiotics, and possibly subconjunctival and parenteral antibiotics, are preferred for endophthalmitis. Parenteral antibiotics are recommended for infection in deep adnexal structures. If infection occurs, culture and sensitivity testing should be undertaken. Medical management, including ophthalmic antibiotics (such as combination aminoglycosides and cephalosporins or fluoroquinolones) or explant can be considered.

7.3.2 TREATMENT OF HYPOTONY

Hypotony is a serious condition that can cause damage to the intraocular tissues and optic nerve. It is a serious risk to ocular health and should be immediately treated when it is persistent or associated with clinical signs. Management of hypotony in BGI implant patients should especially be considered when it is diagnosed at more than 2 visits with IOP <5 mm and when associated concomitant hyptonous findings are noted, including:

- Corneal edema/folds
- Shallow anterior chamber
- Hypotonous maculopathy
- Significant choroidal detachments or effusion

The MicroOptx Brown Glaucoma is designed to achieve normotension in the eye. If hypotony develops in a patient with a BGI implant, inadequate healing and peripheral flow of aqueous humor around the tissue device interface should be suspected. Seidels test will usually confirm the presence or absence of aqueous humor peripheral flow.

If hypotony develops after implantation of the BGI and the subject is confirmed to have central flow of aqueous humor through the device, then the physician may medically manage the hypotony as advised through standard treatment protocols.

Hypotony is best managed by correcting the underlying problem. As a temporizing measure, the anterior chamber may be inflated with viscoelastic or a pars plana injection of viscoelastic or gas may be administered. Steroids may be useful in individuals who are prone to a steroid response, and may improve aqueous humor production by decreasing ciliary body inflammation. Increased fluid intake may slightly increase aqueous humor production.

With inflammatory conditions or with recent surgery or trauma, topical prednisolone acetate or difluprednate may be considered. Additional therapy, such as topical or systemic nonsteroidal anti-inflammatory agents (NSAIDs), systemic, sub-Tenon, or intravitreal steroids, or other systemic medications (eg, methotrexate, cyclosporin), may be appropriate. Because steroids can slow wound healing, use should be moderated in the case of peripheral flow around the tissue device interface.

Atropine and other cycloplegics deepen the anterior chamber, lessen iris-corneal touch, and restore normal anatomy of the lens-iris diaphragm and ciliary body. Unfortunately, atropine also increases the uveoscleral outflow and can contribute to increased choroidal effusion.

If significant persistant hypotony persists, the device can be easily removed and a suture can be placed throught the incisions site. This manuever, as well as pharmacologic treatments as noted above, should allow a prompt resolution of the hypotony.

7.3.3	MANAGEMENT OF DEVICE BLOCKAGE

7.3.4 EXPLANTATION OF THE BROWN GLAUCOMA IMPLANT

The MicroOptx Brown Glaucoma Implant should be explanted if any of the following signs are noted:

- Extreme and persistent ocular discomfort
- Clinically significant infection
- Partial external migration of the BGI associated with site inflammation or nodular hyperplasia
- Significant peripheral flow of aqueous humor along the outside device-tissue interface is seen by Seidel testing
- Significant inflammation associated or possibly associated with the device develops
- Any situation the attending ophthalmologist feels might benefit be improved by device explantation

Explantation in settings of complete and normal healing:

Explantation in the setting of a loose device, one with peripheral flow, infection, etc:

7.3.5 PRECAUTIONARY MEDICATIONS, TREATMENTS, AND PROCEDURES

After implantation of the BGI, intra-ocular pressure should be closely monitored. If pressures fall below 6 mmHg, elimination or reduction of IOP-lowering medications should be considered.

7.3.6 PROHIBITED MEDICATIONS, TREATMENTS, AND PROCEDURES

Any post-implant procedure or treatment that physically interacts with the BGI either on the surface of the eye or in the anterior chamber should be avoided. This excludes any treatments or procedures described in this protocol for treatment of BGI or BGI implant procedure related adverse device effects.

7.3.7 PROPHYLACTIC MEDICATIONS, TREATMENTS, AND PROCEDURES

Study subjects will receive topical antibiotic, corticosteroid, and non-steroid anti-inflammatory (NSAID) agents to begin four times a day, one day prior to surgical implantation of the BGI. These same medicaitons will be used post-operatively for two weeks, and which time they will be reduced to twice daily until the bottles are completely empty or until one month from surgery, whichever comes first.

Bottle size should be 5 ml. The examining surgeon(s) can determine if these medicaitons should be prolonged or reduced any sooner than this protocol.

Study subjects will also receive three sets of drops (to include antibiotic, coriticsteroid, and NSAID) three times between induction and commencement of surgery. The first set of these drops can be given in the pre-operative area of the surgical suite, once IV access is obtained.

8 ASSESSMENT OF SAFETY

8.1 SPECIFICATION OF SAFETY PARAMETERS

All adverse events observed throughout the study will be reported on the Adverse Event CRF.

8.1.1 DEFINITION OF ADVERSE EVENTS (AE)

The following definition is used:

Adverse Event (AE): Any untoward medical occurrence, unintended disease or injury or any untoward clinical signs (including an abnormal laboratory finding) in subjects, users or other persons whether or not related to the investigational medical device.

- NOTE 1: This definition includes events related to the investigational device or the comparator.
- NOTE 2: This definition includes events related to the procedures involved.
- NOTE 3: For users or other persons, this definition is restricted to events related to investigation medical devices.

If an adverse event leads to multiple outcomes that sequentially worsen, only the worst adverse event is reported. For example, abnormal healing leading to infection would be reported as a single AE for the infection.

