The Sponsor and linvestigator will distinguish between the serious adverse events related to the investigational device and those related to the procedures (any procedure specific to the clinical investigation). An adverse event can be related both to procedures and the investigational device. Complications of procedures are considered not related if the said procedures would have been applied to the patients also in the absence of investigational device use/application.

Related to Device - Events reasonably anticipated to be related to the physical presence of the device, e.g. erosion, a device deficiency, dislodgment.

Related to Procedure — Events reasonably anticipated to be related to procedures (pertaining to implant) described in this protocol.

NOTE: Procedure related events refers to the procedure related to the initial application of the investigational medical device only and therefore not to any other procedures or treatments applied later throughout the clinical investigation, for instance to treat (serious) adverse events.

In some particular cases the event may be not adequately assessed because information is insufficient or contradictory and/or the data cannot be verified or supplemented. The Ssponsor and the Investigators will make the maximum effort to define and categorize the event and avoid these situations. Where the Sponsor remains uncertain about classifying the serious event, it should not exclude the relatedness and classify the event as "possible".

Particular attention shall be given to the causality evaluation of unanticipated serious adverse (device) events. The occurrence of unanticipated events related to the use of the device (USADE) could suggest that the clinical investigation places subjects at increased risk of harm than was to be expected beforehand.

All AEs will be collected from the time of informed consent through the end of the study. Death should not be recorded as a separate adverse event, but rather as an outcome of the specific SAE which led to the subject's death. Adverse Events that would be reasonably expected to be associated with any surgical procedure (e.g.: anesthesia associated nausea, surgical site pain) will not be categorized as procedure or device related in the 30 days post the surgical procedure.

Notes:

- 1. Any current condition that is recorded as a pre-existing condition is not an AE, unless there is a worsening of that condition in terms of nature, severity, or degree of incidence.

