8.3 TIME PERIOD AND FREQUENCY FOR EVENT ASSESSMENT AND FOLLOW-UP

Adverse events will be monitored through study closure. Each scheduled and unscheduled follow-up visit will include active ascertainment of new adverse events, as well as follow-up of previously reported, ongoing adverse events. All study subjects will be educated on the anticipated adverse events associated with the BGI and ocular surgery through the consenting process. They will be instructed to contact their physician if they experience any adverse events during their participation in the trial. All adverse events will be documented on the adverse event forms.

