4.1 All AEs and SAEs

The primary summary of safety will consist of all adverse events (AEs), adverse device effects (ADEs), serious adverse events (SAEs), and unanticipated adverse device effects (UADEs) occurring in the implanted eye through 6 months post-implant, by type, summarized by study and overall. For each reported event, the number of events (# Event), number of participants with an event (n), and the percentage of participants among the total sample size (N) will be summarized. Supportive analyses will include summaries of device-related adverse events and secondary surgical interventions through 24 months of follow-up.

Table X. Summary of Adverse Events								
Event	# Events	% (n/N) Participants						
Adverse Events								
Serious Adverse Events								
Device-Related Adverse Events Possibly Probably Definitely Procedure-Related Adverse Events Possibly Probably Definitely								
Study Device and/or Procedure Related Adverse Events								
Serious Study Device and/or Procedure Related Adverse Events								

Table X. Summary of Device-Related Adverse Events					
Participant ID (AE#)	Description of Event	# Events	% (n/N) Participants		

Table X. Summary of Secondary Surgical Interventions						
Participant ID (AE#)	Surgical Intervention	# Events	% (n/N) Participants			

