4.3 Additional Analyses

Signs of inflammation may indicate insufficient healing of the device within the incisional tract, allowing for micromotion of the implant and increase the risk for adverse events, including endophthalmitis. These signs of inflammation include neovascularization around the implant site, conjunctival hyperplasia (mild, moderate and marked), and partial or complete device extrusion.

Analyses will be conducted to determine whether the implant procedure characteristics described in Section 3.3 contribute to increased inflammation, and whether or not the sign of inflammation was elevated to an adverse event. Further, analyses will be performed to determine the association of inflammation with the outcomes of serious adverse events, device occlusion, and explant.

Analyses will also be conducted to determine whether different anti-inflammatory regimens for inflammation have a differential impact on subsequent adverse events, IOP, diminished flow and device useful life.

5. Subgroup Analyses

Key endpoint data (SAE, SAE or explant, IOP) may be assessed according to pre-defined subgroups. These subgroups include:

- Sex (male, female)
- Race (African American, Caucasian, other)
- Implant location (scleral, corneal)
- Allergies with ocular involvement

Other subgroups may be identified in the course of analysis and will be assessed in a *post hoc* fashion.

6. Other Information

In addition to the described data analysis, the following information will also be presented as part of the safety assessment:

- Updated endothelial cell loss (ECL) analysis
- Individual Participant Summaries for each participant
- Line listing of all adverse events
- Line listing of all protocol deviations

Subject # (Eye)	BL ECC	3 mo ECC	6 mo ECC	12 mo ECC	24 mo ECC	3 mo ECC Δ** (%Δ^^)	6 moECC Δ (%Δ)	12 mo ECC Δ (%Δ)	24 mo ECC Δ (%Δ)
##-## (OD)	####	####	####	####	####	+## (#.#)	+## (#.#)	+## (#.#)	+## (#.#)
##-## (OS)	####	####	####	####	####	+## (#.#)	+## (#.#)	+## (#.#)	+## (#.#)

^{*} ND = Not Done

 $^{^{\}wedge}$ NA = Not Applicable

^{**} A positive value indicates higher endothelial cell count relative to baseline reading, while a negative value indicates a loss in endothelial cells (ECL) since baseline

 $^{^{\}wedge \wedge}$ % Δ = (Follow-Up Visit ECC- Baseline ECC)/Baseline ECC * 100

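### Protocol 8.1.1 reports only the worst event of a worsening sequence, so adverse event counts by type are understated, and placement around month 6 is undefined

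*Protocol*

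**What the plan says.** Protocol 8.1.1 defines an adverse event broadly, as any untoward occurrence whether or not device-related, and then adds a collapsing rule: "If an adverse event leads to multiple outcomes that sequentially worsen, only the worst adverse event is reported". It illustrates the rule: "abnormal healing leading to infection would be reported as a single AE for the infection".

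Other parts of the protocol read differently. Section 8.1 says: "All adverse events observed throughout the study will be reported on the Adverse Event CRF". Section 8.2.1 says: "All AEs will be collected from the time of informed consent through the end of the study". Section 8.3 requires, at each scheduled and unscheduled visit, "active ascertainment of new adverse events, as well as follow-up of previously reported, ongoing adverse events". The safety endpoint in the Protocol Summary and in section 4.1.1 is the rate of all adverse events and of the serious and device-related subsets, through the six-month visit.

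SAP 4.1 makes the primary safety summary the events "occurring in the implanted eye through 6 months post-implant, by type, summarized by study and overall". For each type it reports the number of events, the number of participants with an event, and the percentage of the total sample. After month 6 it plans summaries only of device-related events and secondary surgical interventions, to 24 months. SAP 4.3 looks at signs of inflammation and asks, among other things, "whether or not the sign of inflammation was elevated to an adverse event".

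**The concern.** Abnormal healing meets the 8.1.1 definition of an adverse event on its own. The next part of the same section removes it once it leads to something worse. The protocol thus asks for all events and also for only some of them, and two sites could record the same clinical course differently while both comply.

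The affected output is the SAP 4.1 table. In eyes that worsen, the rows for milder events are emptied by rule. The pre-specified list in Protocol 8.1.6 has separate rows that could form such sequences: wound leak, hypotony and hypotony maculopathy; blockage without and then with surgical revision; migration without and then with surgical revision.

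Early events matter in a first-in-human device study. Protocol 2.3.4 reports that every dislodgement seen with earlier versions of the device was preceded by conjunctival hyperplasia and peripheral leakage.

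**Working it through.** The documents give no event figure on this point, and Protocol 10.5 says the sample size of 10 is not statistically derived. There is no stated figure to reproduce, so the check is a count under each possible reading.

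**Inputs.** N = 10 (Protocol 10.5). Month 6 visit window: days 168 to 196 (Protocol 7.2.3). Sequence: abnormal healing then infection (the example in Protocol 8.1.1). The onset days below are assumptions for illustration. The cut-offs tried were days 168 and 196 (the window limits) and day 180 (an assumed midpoint value).

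**Step 1: events lost per sequence.** A sequence of k events is reported as 1, so the loss is k − 1. For the protocol's own two-step example, 2 − 1 = 1 event.

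**Step 2: events inside the 6-month window.**

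| Sequence (assumed days) | All events kept | Worst only, dated at its own onset | Worst only, dated at start of sequence |
|---|---|---|---|
| Abnormal healing day 40, infection day 60 | 2 | 1 | 1 |
| Abnormal healing day 150, infection day 210 | 1 | 0 | 1 (counted as infection) |

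The results are the same at all three cut-offs. For the sequence inside the window, one event is lost under either dating. For the sequence crossing month 6, the count is 0 or 1 depending on a dating convention that neither document gives. If an entry made when abnormal healing was first seen were kept despite the rule, the count would be 1, under the milder term.

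**Step 3: participant rate for the earlier type.** Suppose the participant has no other event of that type in the window. The rate falls from 1/10 = 10% (exact 95% interval 0.3% to 44.5%) to 0/10 = 0% (0% to 30.8%), a drop of 10 percentage points for that row.

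**Step 4: participant rate for any adverse event.** If the whole sequence lies inside the window, this rate does not change, because the participant still has the worst event. It falls by 1/10 only if all of the following hold: the sequence crosses month 6, the single event is dated at the onset of the worst event, no earlier entry is kept, and the participant has no other event in the window.

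**Step 5: how the window is cut.** The protocol runs its endpoint to the six-month visit, while the SAP takes events "occurring in the implanted eye through 6 months post-implant". Neither says whether an event is assigned by onset date or by report date.

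**The case against.** The strongest defence is that 8.1.1 sits in the definition section and sets the counting unit, so that all adverse events elsewhere means all events so counted. The convention is disclosed, illustrated, and used in a small descriptive study with no hypothesis tests. That reading is possible, but it does not restore the counts: the SAP tabulates by type, and the earlier type still loses its event and its participant.

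Other parts of the defence do stand, and they limit the point.

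- A reader might infer that a sequence crossing month 6 leaves nothing in the primary safety window. The documents do not say so. No section dates the single event at the worst outcome or orders an earlier entry to be deleted, and section 8.3 has previously reported events followed up.
- A reader might infer that the SAP 4.3 association between inflammation and serious events is biased towards no association. That analysis uses signs of inflammation, not adverse event records. Signs have their own sources: the scaled implant-site assessment (Protocol 2.3.3), slit lamp findings, and implant-site photographs at every post-implant visit (Table 3). Slit lamp is not scheduled at months 4.5, 8, 10, 15, 18 and 21, but the implant site is still evaluated then. Only the question of whether a sign was raised to an adverse event is affected.
- A reader might infer that the early warning signal is lost altogether. Examination findings are evaluated through six months (Protocol 4.1.1), and individual participant summaries are planned (SAP section 6). These do not feed the SAP 4.1 table, but the information survives.
- A later worst event is not lost if it is device-related or leads to secondary surgery, since SAP 4.1 summarises those to 24 months.
- The halting rule in Protocol 8.7 counts subjects with serious related events. Because the worst event is kept, that count should not normally fall. An exception would be a worst event judged unrelated that follows a related serious one.

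**Conclusion.** The point holds as a counting and reporting defect that should be corrected. The worst-only rule conflicts with Protocol 8.1 and 8.2.1 and with the safety endpoint. Each two-step sequence removes one event from the SAP 4.1 event count and, for the earlier type, one participant: 10 percentage points of that row at N = 10, assuming no other event of the same type in that participant. A sequence crossing month 6 contributes 0 or 1 events to the primary summary, because the date of the single event and the rule for the 6-month cut are both unstated.

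The documents do not support an unconditional 10-point fall in the overall participant rate, which needs every condition in step 4 of the check. How many such sequences will occur cannot be known from the documents, so the total understatement is not estimated here.

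**What to change.** In Protocol 8.1.1, replace the worst-only rule with a requirement that each distinct event in a sequence has its own adverse event line, with onset date, severity, and a link to the event it led to. In SAP 4.1, count events by type in the window of their own onset, and state that the 6-month cut is by onset date. Add a worst-outcome row per participant, which keeps the clinical summary that the present rule appears to want.

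A narrower repair would keep one event per sequence, state which onset date it carries, and define the cut. That settles placement around month 6 but leaves the counts by type understated.

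The cost is a protocol wording change, a linking field on the adverse event form, and a few more lines for ten subjects. The downside is that the counts will look slightly less favourable. Nothing in clinical management changes.
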